Study Description:	Patients with a diagnosis of COVID-19 with critical disease manifestations will be randomly assigned to receive duvelisib or placebo
Objectives:	
Primary Objective: To evaluate the efficacy of duvelisib for the treatment of COVID-19 disease manifestations.
 
Secondary Objectives: To evaluate the safety and tolerability of duvelisib for the treatment of COVID-19 disease manifestations.

Endpoints:	
Primary Endpoint:
 
 • 28 day overall survival 
Secondary Endpoints:
 
 • Hospital and ICU length of stay • Duration of ventilator • Duration of vasopressors • Duration on renal replacement therapy • Viral kinetics • Adverse Events
Study Population:	Twenty-eight patients (approximately 14 per arm) over the age of 18 with a diagnosis of COVID-19 with advanced disease manifestations including one or more of the following: extensive lung involvement, respiratory failure, shock, or cardiac dysfunction.
Phase:	Pilot Phase 2
Description of Sites/Facilities Enrolling:	This is a multi-center study open at Washington University School of Medicine and Missouri Baptist Medical Center.
Description of Study Intervention:	Patients will receive either duvelisib 25mg or placebo for 10 days. Both participants and researchers will be blinded.
Study Duration:	18 months
Participant Duration:	6 months

Table of Contents

PROTOCOL SUMMARY	4
1.0 BACKGROUND AND RATIONALE	7
1.1 COVID-19 and Cytokine Release Syndrome	7
1.2 Lessons and Preclinical Data from CART-related CRS	7
1.3 Gene edited CART model for the Mitigation of CRS	8
1.4 PI3K Inhibition Potently Mitigates CRS in Pre-clinical CART Model.....	9
1.5 PI3K Inhibition to Mitigate Pathogenesis of Advanced COVID-19	10
2.0 OBJECTIVES	11
2.1 Primary Objective	11
2.2 Secondary Objectives.....	11
2.3 Objectives and Endpoints Table	11
3.0 PATIENT SELECTION	12
3.1 Inclusion Criteria	12
3.2 Exclusion Criteria	13
3.3 Inclusion of Women and Minorities	13
4.0 REGISTRATION PROCEDURES	13
4.1 Confirmation of Patient Eligibility	13
4.2 Screen Failures.....	13
5.0 STUDY TREATMENT	14
5.1 Overview.....	14
5.2 Dose Modifications.....	14
5.3 Supportive Care	15
5.4 Viral Load Monitoring.....	17
5.5 Worsening COVID-19 Symptomology	17
5.6 Duration of Therapy.....	17
5.7 Duration of Follow-up	18
5.8 Lost to Follow-Up.....	18
6.0 PHARMACEUTICAL INFORMATION.....	18
6.1 Duvelisib.....	18
7.0 SCHEDULE OF ASSESSMENTS.....	20
8.0 CORRELATIVE STUDIES	22

1.0 BACKGROUND AND RATIONALE

1.1 COVID-19 and Cytokine Release Syndrome

Coronavirus disease 2019 (COVID-19) is an unprecedented international pandemic caused by the severe acute respiratory syndrome coronavirus 2 (SARS-CoV-2).[1] The spread of the virus and the incidence of the disease are accelerating at exponential rates. Despite public health campaigns to quench the spread, delays in testing have allowed for dissemination that is undetected and unaccounted. Aggressive measures are being taken to develop vaccines and therapies, but even relaxation of regulatory measures are unlikely to expedite their development to allow for rapid widespread dissemination. Mortality in patients with severe and critical disease is exceedingly high. In Wuhan, mortality 28-day mortality for those admitted to the ICU was over 60%.[1] In New York City, initial mortality rates for those requiring mechanical ventilation was over 75% for those age 65 years and under, and 97% for those over 65 years-old.[2] These staggering statistics highlight a population with a significant unmet need. It is imperative that existing therapies be evaluated for repurposing in order to manage and potentially reverse the sequela of COVID-19.

Emerging evidence suggests that this novel coronavirus, like others, induces an overactive and ineffective immune cascade associated with acute lung pathology, acute myocarditis, and cytokine storm mediated by cytokines such as interleukins 2, 6, and 8, TNF-alpha, interferon- γ , and G-CSF.[3] This aberrant immune response is thought to be the principal contributor to the morbidity and mortality of COVID-19. Additionally, studies of viral kinetics suggest that viral peaking occurs a number of days prior to the apex of symptoms, further suggesting that decompensation is an immunopathogenic response related to innate immune cells.[4] Numerous anecdotal reports describe the onset of severe symptomatology with refractory pyrexia occurring one to two weeks after initial viral prodrome, consistent with this theory. As such, a number of agents, including IL-6 inhibitors and JAK inhibitors, are aiming to disrupt these immune pathways in COVID clinical trials.

[figure not shown]
[figure not shown]
1.2 Lessons and Preclinical Data from CART-related CRS

Chimeric antigen receptor T-cell (CART) therapy has been limited by life threatening toxicities in over 50% of patients. Toxicities primarily manifest as cytokine release syndrome (CRS) characterized by an early phase with fever, hypotension, increasing oxygen requirements and elevations of cytokines including IFN γ , GM-CSF, TNF, IL-10, and IL-6 and a later phase associated with life-threatening or life-ending neurologic events. IL-6, unlike IFN γ , is often but not always elevated early during CRS and current management strategies rely on administration of the IL-6 receptor antagonist tocilizumab, which is effective at blocking the early events of CRS but ineffective at controlling life threatening CNS CRS.[5] A clinical strategy to prevent CRS without attenuating CART mediated anti-tumor activity is essential for the safe use of CART as a curative therapy for hematological malignancies. Enhancing the safety and efficacy of CART therapy through the amelioration of CRS will dramatically improve outcomes and expand clinical

application of adoptive T cell therapy. The same processes may underlie the terminal clinical manifestations of COVID-19 where patients suffer from progressive fever, increasing oxygen requirements, bleeding and clotting due to the activation of the coagulation cascade and eventual respiratory failure.[6] These events are often associated with elevation of biomarkers such as elevated IL-6, CRP, D-Dimers and ferritin levels, which are comparable to those seen in CART-related CRS.[7]

1.3 Gene edited CART model for the Mitigation of CRS

We hypothesized that the generation of CART cells, engineered through CRISPR/Cas9 gene editing to delete IFN γ , or other selected genes known to mediate inflammatory interactions between CART and target cells and macrophages (source of IL-6 and other inflammatory cytokines) may ameliorate CRS, preventing downstream IL-6 secretion from macrophages. We had previously shown that inhibitors of JAK1/2 could block the production of IL-6 and CRS symptoms when immunocompetent mice were treated with anti-murine CD3 in vivo (Fig 1). We hypothesized that the generation of CART cells, engineered through CRISPR/Cas9 gene editing to delete IFN γ will completely ameliorate CRS, preventing downstream IL-6 secretion from macrophages and dendritic cells. To test

[figure not shown]

[figure not shown]
this hypothesis we developed an in vitro assay to assess the effect of IFN γ deletion in human T cells on the release of CRS related cytokines, specifically IL-6. Using CRISPR/Cas9, IFN γ was genetically deleted in human primary T cells (>80% deletion). IFN γ deficient T cells were stimulated in the presence of immature dendritic cells, prior to cytokine quantification by ELISA (+24hrs). Contrary to expectations, deletion of IFN γ , significantly increased IL-6

secretion from immature dendritic cells. These data suggest that IFN γ is not the key mediator released by activated CART for the induction of IL-6 by iDCs/macrophages (**Fig 2**)

1.4 PI3K Inhibition Potently Mitigates CRS in Pre-clinical CART Model

Using unbiased CRISPR/Cas9 screens in which we have deleted several hundred genes involved in pathways of inflammation in CART19 cells, we have explored several other genes of interest. Although these studies are still in progress we have identified several pathways/genes involving co-stimulatory pathways signaling through phosphoinositide 3-kinase (PI3K) in macrophages. One of these pathways includes the CD40-CD40L pathway. CRISPR/Cas9 genetic deletion of CD40L in CART resulted in normal CART function but no production of IL-6 when incubated with iDC (data not shown). We phenocopied these results by blocking both CD40L on CART and CD40 on iDC using antibodies to each. Of note is that one pathway of CD40 signaling in macrophages includes PI3K signaling specifically PI3K γ signaling. We tested the pharmacologic inhibition of PI3K using a dual PI3K- δ/γ inhibitor duvelisib. Duvelisib, which is currently FDA approved for the treatment of chronic lymphocytic leukemia (CLL) had a potent effect on IL-6 production (even more potent than antibodies to CD40L) while having no impact on CART function, similar to CD40L-CD40 blockade and JAK1/2 blockade (**Fig 3**) Of interest is that the combination of a JAK1/2 inhibitor and duvelisib completely abrogated IL-6 production in our in vitro CAR model (Fig 4).

1.5 PI3K Inhibition to Mitigate Pathogenesis of Advanced COVID-19

PI3K- δ inhibition with duvelisib could potentially avert CRS related to COVID-19, while preserving cytotoxic T-lymphocyte, as we have seen in preclinical work on CART therapy.. Many of the cytokines reduced by duvelisib are ones demonstrated to be significantly elevated in patients with COVID-19, including IL-1 β , IL-6, IL-8, MIP-1 α , MIP-1 β , IL-10, and TNF α , supporting a potential role in mitigating CRS.[8, 9] Duvelisib may also positively impact the respiratory pathology associated with COVID-19 causing acute respiratory distress syndrome. In a murine model of acute pulmonary inflammation, PI3K δ inhibition has been demonstrated to decrease IL-17 production and decrease pathogenic neutrophil recruitment to the lung.[10] Duvelisib has also demonstrated significant reductions in pro-inflammatory cytokines and neutrophil infiltration in in vivo models of asthma and pulmonary inflammation.[11] Lastly, duvelisib may potentiate the elimination of SARS-CoV-2 through preferential macrophage polarization and inhibiting viral persistence. Duvelisib has been demonstrated to polarize macrophages to the M1 phenotype which is responsible for pathogen elimination.[12] Such macrophage polarization has been demonstrated in primary samples from clinical trials of duvelisib.[13] Additionally, PI3K/Akt signaling has been shown to be a requirement for persistent SARS-CoV-1 infection in vitro in Vero E6 cells, which inhibition of PI3K can disrupt.[14, 15]

The exceedingly high mortality rates of severe and critical COVID-19 warrant the identification and evaluation of novel therapies that could potentially mitigate the advanced disease manifestations. Based on preclinical data from our institution and others, we hypothesize that PI3K inhibition with duvelisib could potentially quell aberrant hyperactivation of the innate immune system, preferentially polarize macrophages, reduce pulmonary inflammation, and limit viral persistence, thereby improving patient outcomes.

2.0 OBJECTIVES

2.1 Primary Objective

To evaluate the efficacy of duvelisib for the treatment of COVID-19 disease manifestations.

2.2 Secondary Objectives

To evaluate the safety and tolerability of duvelisib for the treatment of COVID-19 disease manifestations.

2.3 Objectives and Endpoints Table

Objectives	Endpoints	Justification for Endpoints
Primary		
To evaluate the efficacy of duvelisib for the treatment of COVID-19 disease manifestations.	Primary: 28 day overall survival	The expected survival of these patients with advanced COVID-19 symptoms is poor and studies are currently needed.
	Secondary: Hospital and ICU length of stay and duration of ventilator, vasopressors, and renal replacement therapy	In addition to improving survival, duvelisib may reduce the need for these interventions.
Secondary		
To evaluate the safety and tolerability of duvelisib for the treatment of COVID-19 disease manifestations.	Viral kinetics	Duvelisib and similar treatments which modulate cytokine signaling have the potential to reduce immune function which could result in increasing viral loads.
	Adverse events	Adverse events are common with duvelisib for its indicated purpose. It is unclear if similar adverse events are observed in this population.

3.0 PATIENT SELECTION

3.1 Inclusion Criteria

1. A diagnosis of advanced COVID-19 as defined both of the following:
 - a. as a positive test for SARS-CoV-2 RNA detected by RT-PCR collected from the upper respiratory tract (e.g. nasopharyngeal, nasal, oropharyngeal swab, or saliva) and, if possible, the lower respiratory tract (sputum, tracheal aspirate, or bronchoalveolar lavage), analyzed by a CLIA certified lab with an FDA approved assay. [11]
 - b. Critical disease manifested by any of the following:
 - i. Chest imaging with $\geq 50\%$ lung involvement
 - ii. Respiratory failure requiring invasive mechanical ventilation, non-invasive mechanical ventilation (eg. BiPAP, OptiFlow), supplementary oxygen with ≥ 6 LPM, or extracorporeal membrane oxygenation (ECMO)
 - iii. Shock – defined as mean arterial pressure ≤ 65 mmHg unresponsive to 25ml/kg isotonic intravenous fluid resuscitation and/or requiring vasopressor support (See Appendix A)
 - iv. Cardiac dysfunction defined by:
 1. New global systolic dysfunction with ejection fraction $\leq 40\%$
 2. Takotsubo cardiomyopathy
2. Patients who have received prior investigational or off-label agents for COVID-19 does not exclude eligibility.
3. At least 18 years of age at the time of study registration
4. Adequate hematologic function defined as absolute neutrophil count $\geq 1000/\text{mm}^3$ and platelet count $\geq 50,000/\text{mm}^3$ without growth factor or transfusion support for 7 days prior to screening.
5. Creatinine-clearance ≥ 15 mL/minute or receiving renal replacement therapy (See Appendix B)
6. Aminotransferase (AST/ALT) levels $<3x$ the upper limit of normal
7. Able to understand and willing to sign an IRB approved written informed consent document (or that of legally authorized representative, if applicable)
8. Women of childbearing potential (defined as women with regular menses, women with amenorrhea, women with irregular cycles, women using a contraceptive method that precludes withdrawal bleeding, or women who have had a tubal ligation) are required to have a negative pregnancy test and use two forms of acceptable contraception, including one barrier method, during participation in the study treatment period.

9. Male patients if engaging in sex with a women of childbearing potential are required to use two forms of acceptable contraception, including one barrier method, during participation in the study and throughout the evaluation period.

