3.2 Exclusion Criteria

1. Known allergy or intolerance to duvelisib or another PI3K inhibitor.
2. Known or suspected active viral (including CMV, HIV, hepatitis B, and hepatitis C), bacterial, mycobacterial, or fungal infection other than COVID-19. CMV viral load will be assessed at screening and those with viremia will be excluded. Other virologic testing not required unless infection is suspected.
3. Pregnant and/or breastfeeding.
4. Any uncontrolled intercurrent illness that would put the patient at greater risk or limit compliance with study requirements in the opinion of the investigator.

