5.0 STUDY TREATMENT

5.1 Overview

Patients will be randomly assigned in a double-blind fashion to receive either duvelisib 25mg or placebo twice daily for up to 10 days. Patients who have significant clinical improvement prior to day 10 and are going to be discharged from the hospital may discontinue the treatment early with investigator permission.

Blocks of 10 patients will be used to allocate patients to duvelisib or placebo. Due to differences in color between the duvelisib and placebo capsules, we will employ methods in this trial to maintain the blinding of the investigator to the best of our ability (e.g. having the drug dispensed by alternative personnel). If this study were to lead to a pivotal trial, matched placebos would be manufactured for such a trial.

Treatment is dosed orally and can be administered with or without food. For patients unable to administer orally, a duvelisib suspension will be administered through a nasogastric/orogastric tube. In this event, the capsule(s) will be opened and the dose will be placed in 40mL water and stirred until dissolved. The suspension should be administered using an appropriate syringe within 6 hours after preparation. Following administration, the tube should be rinsed with approximately 75 mL of water.

If a dose is missed by fewer than 6 hours, administer the missed dose right away and take the next dose as usual. If a dose is missed by more than 6 hours, the patient should not take an additional dose, but should take the next usual prescribed dose.

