5.3.4 Investigational or Off-Label Treatments for COVID-19

Patients who have received other investigational or off-label agents previously are eligible for study and these agent(s) may be continued at the discretion of the treating physician.

During study treatment, screening through Day 10, the addition of investigational or off-label agents for patients on the study is discouraged. However, physicians who believe use of such agents is warranted should discuss with the principal investigator. If such agents are administered, patients are permitted to continue on duvelisib.

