5.6 Duration of Therapy

If at any time the constraints of this protocol are considered to be detrimental to the patient's health and/or the patient/surrogate no longer wishes continuation of the protocol therapy, the protocol therapy should be discontinued and the reason(s) documented in the case report forms.

Patients will be removed from the study for any of the following reasons:

- Death
- Adverse event(s) that, in the judgment of the investigator, may cause severe or permanent harm or which rule out continuation of the study drug
- General or specific changes in the patient's condition that render the patient unacceptable for further treatment in the judgment of the investigator
- Suspected pregnancy
- Serious noncompliance with the study protocol

- Lost to follow-up
- Patient/surrogate withdraws consent
- Investigator removes the patient from study
- Investigator decides to close the study

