5.7 Duration of Follow-up

All patients will be followed as according to the protocol calendar in Section 7.0 for the duration unless the patient withdraws consent or is lost-to-follow-up. Following the safety follow-up visit, patients will continued to be monitored for survival and late-onset toxicity every 3 months for up to 6 months. For these long-term follow-up visits, a telephone visit can be made in lieu of a physical visit.

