7.0 SCHEDULE OF ASSESSMENTS

	Screening ¹	Study Treatment Days											Safety Follow-Up ¹¹	
		-1	1	2	3	4	5	6	7	8	9	10	15	29
Informed Consent	X													
Medical History	X													
Physical Exam w/ vital signs and O2 saturation ²	X	X	X	X	X	X	X	X	X	X	X	X	X	X
APACHE II Score		X										X		
SOFA Score		X										X		
CBC ²	X	X	X	X	X	X	X	X	X	X	X	X	X	X
CMP ²	X	X	X	X	X	X	X	X	X	X	X	X	X	X
Ferritin ²	X	X	X	X	X	X	X	X	X	X	X	X	X	X
D-Dimer ¹⁰	X		X	X		X				X			X	X
aPTT and PT/INR ¹⁰	X		X	X		X				X			X	X
Fibrinogen ¹⁰	X		X	X		X				X			X	X
C-reactive peptide ²	X	X	X	X	X	X	X	X	X	X	X	X	X	X
SARS-CoV-2 viral load ³	X	X	X	X	X	X	X	X	X	X	X	X	X	X
Quantitative immunoglobulins (IgA, IgG, IgM)	X													
Immune competence assessment	X													X
CMV IgG	X													
CMV DNA PCR (CMV seropositive pts)	X									X ⁸				
Serum βhCG ⁴	X													
Chest X-ray ⁵	X													
Electrocardiogram ⁵	X													
ECHO or MUGA ⁵	X													
Plasma troponin and NT-proBNP ⁵	X													
Duvelisib/placebo ⁶			X	X	X	X	X	X	X	X	X	X		
PJP prophylaxis ⁷			X	X	X	X	X	X	X	X	X	X	X	X

Correlative studies ⁹	X ¹²			X		X				X		X	X	X
Adverse event monitoring			Continuously											

- 1 – Within 7 days of registration
- 2 – Performed daily while inpatient or per local SOC. If outpatient, visits may occur within +/- 2 days from schedule
- 3 – Performed daily through Day +10 then weekly thereafter by NP or OP
- 4 – Women of childbearing potential only
- 5 – Not required at Screening if patient meets Inclusion Criterion 1 by other measures. Repeated on study if clinically indicated.
- 6 – Duvelisib or placebo will be administered twice daily for up to 10 days. See section 5.0 for treatment administration details.
- 7 - Continued until CD4+ T cells >200 cells/μL. Choice of agent per institutional guidelines and patient tolerance.
- 8 – CMV viral load monitoring should occur at screening, and on D8 in patients who are CMV seropositive (positive IgG at screening). CMV prevention/treatment should follow institutional guidelines.
- 9 – Collected on the first 10 patients enrolled onto study. A variance of +/- 2 days for correlative collection will be permitted.
- 10 – Performed as scheduled or more frequently if clinically indicated for coagulopathy monitoring

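### Inclusion 8 ends women's contraception with study treatment (Day 10 at most), a shorter-worded duty than men's, and gives no reason for leaving the 30-day pregnancy-reporting period uncovered

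*Combined protocol and SAP*

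**What the plan says.** **Women.** Section 3.1, item 8, asks women of childbearing potential for a negative pregnancy test and to "use two forms of acceptable contraception, including one barrier method, during participation in the study treatment period".

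**Men.** Item 9 asks men who have sex with a woman of childbearing potential for the same methods, but "during participation in the study and throughout the evaluation period". The evaluation period is not defined.

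**End of treatment.** Section 5.1 limits dosing to 10 days, and patients who improve and are about to be discharged "may discontinue the treatment early with investigator permission". Section 5.3.4 describes the period as "During study treatment, screening through Day 10". The schedule in Section 7.0 places Days 15 and 29 under safety follow-up, apart from the treatment days.

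**Pregnancy reporting.** Section 10.1.2 makes pregnancies in participants, or in partners of male participants, immediately reportable up to 30 days after the last dose. Appendix D gives the same 30 days in its expedited table. Section 10.1.2 also states that duvelisib has not been studied in pregnant or nursing women, and that treating women of childbearing potential who do not use highly effective contraception is contraindicated.

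**Safeguards.** Section 3.2 excludes patients who are "Pregnant and/or breastfeeding". Section 5.6 lists "Suspected pregnancy" as a reason for removal. Under Section 5.7 patients are "monitored for survival and late-onset toxicity every 3 months for up to 6 months". Serum βhCG ("Women of childbearing potential only") is marked at screening only.

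**The concern.** A woman who recovers and goes home can follow item 8 exactly and still conceive while the plan is monitoring for drug-exposed pregnancies. She took the study drug herself, yet her duty is worded more narrowly than that of a male participant, and the protocol gives no reason. The safeguards listed above screen for a pregnancy, detect it or manage it. None asks for prevention once treatment is over.

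What is at stake is the safety of a few participants and possible in-utero exposure to a drug not evaluated in pregnancy. The trial's statistical conclusions are not at stake.

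**Working it through.** The plan has no figure to reproduce. The check is a day count and a comparison of texts.

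**Inputs**
- Day of last dose, d = 1 to 10 (Section 5.1; Section 7.0).
- Reporting window ends on Day d + 30 (Section 10.1.2; Appendix D).
- End of the women's duty: item 8 ties it to the treatment period, which can be read in two ways when treatment stops early.
- Last safety visit: Day 29 (Section 7.0).

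**End of the reporting window**
- d = 1: 1 + 30 = Day 31.
- d = 10: 10 + 30 = Day 40.

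**Days reportable but not covered by item 8**
- Reading A, the treatment period ends with the last dose: (d + 30) − d = 30 days for every d.
- Reading B, the treatment period runs to Day 10 regardless: (d + 30) − 10 = d + 20. This is 21 days at d = 1, 29 at d = 9 and 30 at d = 10.
- A full course gives 30 days on both readings. An early stop gives 21 to 30.

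**Against the visit schedule**
- The window closes 31 − 29 = 2 to 40 − 29 = 11 days after the Day 29 visit, when adverse-event tracking also ends (Section 10.0).
- Scheduled pregnancy tests after screening: 0.
- Outpatient Day 15 and Day 29 visits may be by telephone without laboratory tests, but only where circumstances rule out attendance in person (Section 7.0, footnote 11).

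**Days at home inside the window**

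This applies to a full course, using 40 − discharge day. The discharge days are illustrative assumptions; the documents give none.

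| Discharge day | Days at home inside the window |
|---|---|
| 10 | 30 |
| 15 | 25 |
| 20 | 20 |
| 29 | 11 |
| 40 | 0 |

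**Number exposed**

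Accrual is 28, about 14 per arm (Section 12.0). The documents do not say how many will be women of childbearing potential. With equal arms, about half of them would receive duvelisib.

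**Items 8 and 9 side by side**

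The women's rule covers the treatment period. The men's rule covers study participation plus the evaluation period. Because that last term is undefined, the difference cannot be given in days; only the direction of the wording is clear.

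**The case against.** The strongest reply is that nothing here conflicts. Item 8 is a prevention rule and Section 10.1.2 is a pharmacovigilance rule owed to the drug supplier. A reporting window may sensibly outlast a prevention window, because its purpose is to catch late events, and both rules can be obeyed as written. This stands. A reader might infer that the protocol contradicts itself; it does not.

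A reader might also infer that 30 days of contraception is medically required. The documents do not support that. They give no half-life, washout or embryo-fetal data, and the contraindication in Section 10.1.2 concerns treatment and sets no post-dose period. The right period could be shorter or longer than 30 days, or even none. The consent pages and the investigator's brochure were not available and may say more.

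A third tempting inference is that the methods in item 8 fall short of Section 10.1.2. Item 8 asks for acceptable methods and Section 10.1.2 for highly effective ones, but neither term is defined. Two forms including a barrier therefore cannot be shown to be inadequate. During treatment item 8 is demanding, and its definition of childbearing potential is broad.

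Finally, the group is tiny. Patients are critically ill, many will be in hospital or will have died for part of the window, and only about half of the eligible women would receive the drug. This limits the weight of the point but does not remove it: Section 5.1 itself foresees discharge before Day 10, and entry is open to patients who are not ventilated.

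**Conclusion.** The point holds as a cheap patient-safety improvement and not as an error. The protocol text asks women for no contraception beyond treatment, words their duty more narrowly than men's, and gives no reason for either. The period left open is 30 days after a full course, or 21 to 30 days after an early stop, measured against the plan's own reporting window.

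That measure assumes only that the window is a reasonable default for the period in which the sponsor considers exposure relevant. It is not evidence of risk on any given day. The number of women affected is not in the documents and is probably very small. The primary endpoint, power and analysis are unaffected. The conclusion covers the protocol text only.

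**What to change.** In item 8, require contraception during treatment and until 30 days after the last dose, or longer if the drug maker's data require it. State the same period in Section 10.1.2. In the same edit, use the Section 10.1.2 term, highly effective, and define it once. Defining the evaluation period in item 9 would make the two items comparable.

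Apply the rule to both arms, since allocation is blinded.

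The cost is one sentence in item 8, the eligibility checklist and, if needed, the consent form. For participants it is up to 30 more days of contraception for a few women. No visit, sample-size figure or analysis changes.
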